1 LIST OF ABBREVIATIONS

Abbreviation	Definition
ADE	Adverse Device Effect
AE	Adverse Event
ANCOVA	Analysis of Covariance
ASADE	Anticipated Serious Adverse Device Effect
BMI	Body Mass Index
CI	Confidence Interval
CRF	Case Report Form
EQ-5D-5L	EuroQol (European Quality of Life) five-dimensional Five-level
FAS	Full Analysis Set
HOOS JR	Hip disability and Osteoarthritic Outcome Score for Joint Replacement
HRQoL	Health Related Quality of Life
ITT	Intent to Treat
LL	Lower Limit
LSMean	Least Square Mean
MI	Multiple Imputation
NA or N/A	Not Applicable
N (or n)	Total Sample Size (or subgroup sample size)
NMPA	National Medical Products Administration
РР	Per-protocol Population
PROM	Patient Reported Outcome Measure
QoL	Quality of Life
S&N	<smith &="" inc.,="" j.="" ltd.="" nephew="" orthopaedics="" smith="" t.=""></smith>
SAP	Statistical Analysis Plan

CONFIDENTIAL AND PROPRIETARY

Statistical Analysis Plan

A Prospective, Multi-center, Randomized, Controlled Study to Evaluate the Safety and Efficacy of the OR3O[™] Dual Mobility System versus conventional single bearing design Total Hip System in Primary Total Hip Arthroplasty (THA) Procedures Version: 2.0, 29-Feb-2024 Page: 5 of 27

Number: OR3O.2019.10 ST: 1100 Version: 2.0, 29-Feb-2024 Page: 5 of 27

Abbreviation	Definition
SADE	Serious Adverse Device Effect
SAE	Serious Adverse Event
SAF	Safety Analysis Population
SE	Standard Error
TFL	Tables, Figures and Listing
THA	Total Hip Arthroplasty
UL	Upper Limit
USADE	Unanticipated Serious Adverse Device Effect
VAS	Visual Analogue Scale

CONFIDENTIAL AND PROPRIETARY

Statistical Analysis PlanNumber: OR30.2019.10
ST: 1100A Prospective, Multi-center, Randomized, Controlled Study to Evaluate the
Safety and Efficacy of the OR30™ Dual Mobility System versus conventional
single bearing design Total Hip System in Primary Total Hip Arthroplasty (THA)Number: OR30.2019.10
ST: 1100ProceduresPage: 6 of 27

2 INTRODUCTION

This statistical analysis plan (SAP) is written to specify in greater detail, the statistical analyses that will be carried out as outlined in OR3O study protocol ID: OR3O.2019.10 version 1.0 dated 18-Aug-2020. The contents of this SAP and its accompanying tables, figures and listings (TFLs) mockups will serve as guideline for programming the TFLs that will summarize the study data.

If modifications to the analyses specified herein or additional analyses required prior to reporting, these would be detailed either in an addendum to the SAP or in an amended SAP.

3 STUDY DESIGN

This study is a prospective, multi-center, randomized, controlled, 2-arm study planned to assess safety and efficacy of the OR3O[™] Dual Mobility System in Primary THA. Subjects who meet the pre-specified inclusion/exclusion criteria in the protocol will be randomized to receive implantation with either the investigational product or controlled system. Up to 4 sites in China will participate competitive enrolling a total of 170 hips.

The study is expected to enroll all subjects within a 12 month timeframe. Subjects will be postoperatively followed-up at 6 weeks, 3, 6, 12 and 24 months. In this study, a summary of 1 year follow-up data will be reported to National Medical Products Administration (NMPA) for regulatory approval and a 2 year follow-up will be sufficient to identify and assess the risk of any associated unacceptable adverse event over this time period. The study duration will be sufficient to allow conclusions about likely safety and efficacy of the OR3O Dual Mobility System in a longer term.

CONFIDENTIAL AND PROPRIETARY

Statistical Analysis Plan

A Prospective, Multi-center, Randomized, Controlled Study to Evaluate the Safety and Efficacy of the OR3O[™] Dual Mobility System versus conventional single bearing design Total Hip System in Primary Total Hip Arthroplasty (THA) Procedures Version: 2.0, 29-Feb-2024 Page: 7 of 27

Figure 1 describes and details the different steps of study conduct from screening to enrollment and follow-up while Table 1 provides details of the study's schedule of events.

Figure 1: Study Flowchart

CONFIDENTIAL AND PROPRIETARY

This document contains information that is confidential and proprietary to Smith & Nephew PLC and Smith & Nephew, Inc. and is intended for use only by Smith+Nephew and its manufacturer. It shall not be reproduced or copied in whole or in part, nor shall the contents be disclosed by any means without prior written permission from Smith+Nephew, nor shall anyone make any use of it that is contrary to the expressed or implied wishes of Smith+Nephew.

Number: OR3O.2019.10 ST: 1100 Version: 2.0, 29-Feb-2024 Page: 7 of 27

Statistical Analysis PlanNumber: OR3O.2019.10A Prospective, Multi-center, Randomized, Controlled Study to Evaluate the
Safety and Efficacy of the OR3O™ Dual Mobility System versus conventional
single bearing design Total Hip System in Primary Total Hip Arthroplasty (THA)Number: OR3O.2019.10
ST: 1100
Version: 2.0,
29-Feb-2024
Page: 8 of 27ProceduresProcedures

Table 1: Study Schedule of Events

Schedule of events	Pre- Operative Data	Operative / Discharge	6 Weeks (42 – 7/+14 days)	3 mos (90 ± 30 days)	6 mos (180 ± 30 days)	1 yr. (365 ± 60 days)	2 yr. (730 ± 60 days)
Informed Consent	х						
Inclusion/ Exclusion	х						
Demographics	х						
Medical History	х						
Vital Signs	х						
Preoperative Lab Examinations (eg. Blood Routine Examination, Biochemical Examination, Coagulation Examination) ⁽¹⁾	x						
Pregnancy Test ⁽²⁾	х						
Operative Data		x					
Discharge Data		x					
Implant status			х		х	х	х
HHS	х		Х	х	х	х	Х
EQ-5D-5L	х		Х	х	х	х	х
HOOS JR.	х		Х	х	х	х	х
Radiographic Assessment	(x) ³	(x) ⁴	(x) ⁴	х	х	Х	х
Concomitant Medications ⁽⁵⁾		x	Х	х	Х	Х	х
Safety Assessment (AEs, DDs)		x	Х	х	х	х	х
End of Study/ Exit		x	х	х	х	х	х

¹ If applicable, where, for preoperative lab examinations, only those within Day 0~14 before the operation are acceptable. The Preoperative Lab Examinations required to be performed include:

Blood routine examination: Haemoglobin, Platelet count, White Blood Cell count, neutrophil count, erythrocyte sedimentation rate

- Coagulation examination: Prothrombin time, activated partial thromboplastin time), thrombin time, D-dimer
- Biochemical examination: Urea or urea nitrogen, creatinine, AST, ALT, blood glucose
- > Other examination: Erythrocyte sedimentation rate, C-reactive Protein

² If applicable, where, the pregnancy test is only suitable for females of child-bearing potential, neither premenstrual females nor sterilized or postmenopausal (i.e., 12-month amenorrhea without alternative medical reasons) females.

³ If X-ray image has been done within 30 days before the Informed Consent Form is signed, and the data is available, they can be used as the data for screening before operation.

⁴ Radiographic assessment performed at discharge or 6 week follow-up visit only.

⁵ All combination medications associated with AEs or serious adverse events (SAEs) are reported.

CONFIDENTIAL AND PROPRIETARY

Statistical Analysis Plan

A Prospective, Multi-center, Randomized, Controlled Study to Evaluate the
Safety and Efficacy of the OR3O[™] Dual Mobility System versus conventional
single bearing design Total Hip System in Primary Total Hip Arthroplasty (THA)Version: 2.0,
29-Feb-2024
Page: 9 of 27ProceduresProcedures

5 STUDY OBJECTIVES

5.1 Primary Objective

The primary objective of this study is to assess safety and efficacy of the OR3O[™] Dual Mobility System in Primary THA at 1 year postoperative.

5.2 Secondary Objectives

The secondary objectives of this study are to assess safety and efficacy of the OR3O[™] Dual Mobility System and compatible components in Primary THA up to 2 years after surgery.

5.3 Exploratory Objectives

Other objectives of the study are to assess the hip dislocation percentage and hospital readmission percentage (cumulative) up to 2 years after device implantation.

STUDY ENDPOINTS

5.4 Primary Endpoint

The primary endpoint is proportion of excellent (\geq 90) or good (80-89) HHS scores at 12 month postoperative.

5.5 Secondary Endpoints

Safety and efficacy evaluated in this study at baseline, 6 weeks, 3 months, 6 months, 1 year and 2 years after surgery as measured by:

TMP-CD-30-01 Statistical Analysis Plan – Revision B; SOP-CD-30 Statistical Analysis

Number: OR30.2019.10 ST: 1100 Version: 2.0, 29-Feb-2024 Page: 9 of 27

CONFIDENTIAL AND PROPRIETARY

This document contains information that is confidential and proprietary to Smith & Nephew PLC and Smith & Nephew, Inc. and is intended for use only by Smith+Nephew and its manufacturer. It shall not be reproduced or copied in whole or in part, nor shall the contents be disclosed by any means without prior written permission from Smith+Nephew, nor shall anyone make any use of it that is contrary to the expressed or implied wishes of Smith+Nephew.

Statistical Analysis Plan

A Prospective, Multi-center, Randomized, Controlled Study to Evaluate the
Safety and Efficacy of the OR3O[™] Dual Mobility System versus conventional
single bearing design Total Hip System in Primary Total Hip Arthroplasty (THA)Version: 2.0,
29-Feb-2024
Page: 10 of 27
Procedures

- Number: OR3O.2019.10 ST: 1100 Version: 2.0, 29-Feb-2024) Page: 10 of 27
- Survivorship of the OR3O[™] Dual Mobility System (no revision due to any reason)
- Survivorship of controlled system (assessed by revision for any reason) (no revision due to any reason)
- Harris Hip Score (HHS)
- EuroQol (European quality of life) five-dimensional Five-level (EQ-5D-5L) score
- Hip Disability and Osteoarthritis Outcome Score for Joint Replacement (HOOS JR.)
- Radiographic Assessment
 - Implant position/Orientation
 - Implant subsidence/migration
 - Periprosthetic fractures
 - Heterotopic ossification
 - Radiolucencies
 - o Osteolysis
 - Implant loosening
 - Stress Shielding

5.6 Exploratory Endpoints

The following exploratory endpoints will be collected:

- Dislocation percentage of the hip up to 2 years after device implantation.
- Hospital readmission percentage (cumulative) within 30, 60 and 90 days of discharge due to any reason related to study device or study procedure.

5.7 Safety Endpoints

Safety endpoints include the collection of the following events:

• All adverse events (AEs) occurring from the time of subject enrollment until study termination or study completion including intra-operative adverse events.

CONFIDENTIAL AND PROPRIETARY

This document contains information that is confidential and proprietary to Smith & Nephew PLC and Smith & Nephew, Inc. and is intended for use only by Smith+Nephew and its manufacturer. It shall not be reproduced or copied in whole or in part, nor shall the contents be disclosed by any means without prior written permission from Smith+Nephew, nor shall anyone make any use of it that is contrary to the expressed or implied wishes of Smith+Nephew.

Statistical Analysis Plan

A Prospective, Multi-center, Randomized, Controlled Study to Evaluate the
Safety and Efficacy of the OR3O[™] Dual Mobility System versus conventional
single bearing design Total Hip System in Primary Total Hip Arthroplasty (THA)Version: 2.0,
29-Feb-2024
Page: 11 of 27
Procedures

Number: OR3O.2019.10 ST: 1100 Version: 2.0, 29-Feb-2024 Page: 11 of 27

• Device Deficiencies.

6 STATISTICAL CONSIDERATIONS

6.1 Determination of Sample Size

Sample size calculation is based on the assumption that in order to be considered of comparable efficacy, study arm (dual mobility cohort) must obtain at least 90% of the efficacy in the controlled arm (conventional cohort). It is expected and further assumed that 95% of the Harris Hip Score at 12 months postoperative will have a rating of good or excellent (80-89, \geq 90), then 76 evaluable subjects per group would be required to carry out the hypothesis testing at 12 months postoperatively. Assuming an attrition rate of 10% at 1 year, 85 subjects are needed per arm. It is planned to have 4 sites enroll on average, 43 subjects per investigational site and a min. of 20 subjects should be enrolled per site (overall subjects enrolled in the study of 170).

6.2 Randomisation

Subjects meet all inclusion/exclusion criteria will be randomly allocated into any of two study groups (study arm or controlled arm) in a 1:1 allocation ratio. Blocked randomization to balance this allocation ratio by investigational site and overall will be implemented through a network-based randomization system. A randomization number is allocated only when subjects have signed the Informed Consent Form and satisfy all study eligibility criteria.

6.3 Interim Analysis

An interim analysis is planned to be carried out after completion of all 1 year follow-up visits in order to support the China NMPA registration. Additional interim analyses might be performed as and when

CONFIDENTIAL AND PROPRIETARY

This document contains information that is confidential and proprietary to Smith & Nephew PLC and Smith & Nephew, Inc. and is intended for use only by Smith+Nephew and its manufacturer. It shall not be reproduced or copied in whole or in part, nor shall the contents be disclosed by any means without prior written permission from Smith+Nephew, nor shall anyone make any use of it that is contrary to the expressed or implied wishes of Smith+Nephew.

Statistical Analysis Plan

A Prospective, Multi-center, Randomized, Controlled Study to Evaluate the Version: 2.0, Safety and Efficacy of the OR3O[™] Dual Mobility System versus conventional single bearing design Total Hip System in Primary Total Hip Arthroplasty (THA) Page: 12 of 27 Procedures

Number: OR30.2019.10 ST: 1100 Version: 2.0, 29-Feb-2024 Page: 12 of 27

needed to support and maintain product registration in different markets globally. At minimum, preoperative, demographic and PROMS data will be summarized for interim analyses.

7 STATISTICAL ANALYSIS

The Full Analysis Set (FAS) population will be used to summarize the primary and all secondary endpoints (excluding radiographic assessments) while the Safety (SAF) population will be used summarize all safety and exploratory endpoints. The SAF population will additionally be used to summarize radiographic assessments The Per Protocol (PP) population will additionally be used to summarize the primary endpoint.

7.1 General

All statistical comparisons of the data will indicate the test statistic used as well as its distributional assumptions. Unless otherwise stated, all statistical significance tests will be two-sided, performed at the 5% significance level (i.e. $\alpha = 0.05$). Where appropriate, the resulting p-values will be quoted and if applicable, the corresponding 95% two-sided confidence intervals (CIs) will also be generated. All p-values will be rounded to three decimal places; p-values less than 0.001 will be presented as `<0.001' in all tables.

For data summaries, categorical and ordinal variables will be summarized using frequency (n) and percent (%). Continuous variables will be summarized using characteristics such as number of observations, mean, median, standard deviation, minimum and maximum values.

7.2 Analysis Populations

The following section details the analysis populations:

TMP-CD-30-01 Statistical Analysis Plan - Revision B; SOP-CD-30 Statistical Analysis

CONFIDENTIAL AND PROPRIETARY

This document contains information that is confidential and proprietary to Smith & Nephew PLC and Smith & Nephew, Inc. and is intended for use only by Smith+Nephew and its manufacturer. It shall not be reproduced or copied in whole or in part, nor shall the contents be disclosed by any means without prior written permission from Smith+Nephew, nor shall anyone make any use of it that is contrary to the expressed or implied wishes of Smith+Nephew.

Statistical Analysis Plan

A Prospective, Multi-center, Randomized, Controlled Study to Evaluate theVersion: 2.0,Safety and Efficacy of the OR3O[™] Dual Mobility System versus conventional29-Feb-2024single bearing design Total Hip System in Primary Total Hip Arthroplasty (THA)Page: 13 of 27ProceduresProcedures

Number: OR3O.2019.10 ST: 1100 Version: 2.0, 29-Feb-2024 Page: 13 of 27

Safety (SAF) Population: This is defined as all hips who have been implanted with the OR3O[™] Dual Mobility System or controlled system. The SAF population will be based on the device that is implanted into the hip and not the one the hip is randomized to (if different).

Full Analysis Set (FAS) Population: This is defined according to the basic principle of Intent-to-Treat (ITT) principle i.e., all implanted hips with at least one postoperative effectiveness, HRQoL or performance will be included in FAS Population.

Per-Protocol (PP) Population: The PP population is the subset of hips in the FAS population who do not have major protocol deviations and who satisfied all enrollment eligibility criteria. Criteria that can be regarded as major deviations will be formally classified on a case-by-case basis prior to the final study database lock.

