7.6 ENROLLMENT

The site initiation shall be started only after the EC has approved and the clinical trial agreement has signed at each site. Subjects for whom the consent process has been completed and have been implanted with the study product are considered enrolled. Competitive enrollment continues until the completion of enrolled 170 subjects.

If the subject does not have the OR3O™ Dual Mobility System or controlled system implanted after signing an informed consent form, the subject will be considered to be a Screen Failure. Screen Failures will not count into the total number of enrolled subjects.

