7.8 WITHDRAWAL

7.8.1 Withdrawal from Treatment

Subjects may be withdrawn from having the study device implanted at a date close to surgery or during surgery for the following reasons:

- At the discretion of the Investigator due to:
 - A change in treatment being clinically warranted.
 - An adverse event.
 - Any other significant reason identified by the Investigator.

Subjects who provide informed consent but do not receive the study device for any reason will be considered a Screen Failure. Screen Failures will not count into the total number of enrolled subjects.

If at any point during the study, the study device needs to be revised for any reason the following will apply: Intraoperative data from the revision surgery will be collected including implant information used for revision THA. Subjects will terminate the study following revision surgery. Subjects shall be followed by the Investigator according to sites' standard of care in order to monitor the subject's health status and the outcome of the revision. Data collected following the revision surgery will be reported as follow-up data to the adverse event. Data will not be included as study data but presented separately as safety data. Data collected upon the point of revision will be included as study data.

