8.5.2 Randomization

Subjects meet all inclusion/exclusion criteria will be randomly allocated into any of two study groups (study arm or controlled arm) in a 1:1 allocation ratio. Blocked randomization to balance this allocation ratio by investigational site and overall will be implemented through a network-based randomization system. A randomization number is allocated only when subjects have signed the Informed Consent Form and satisfy all study eligibility criteria.

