10.2 ANALYSIS POPULATIONS

The following section details the analysis populations:

- Safety (SAF) Population: This is defined as all hips who have been implanted with the OR3O™ Dual Mobility System or controlled system.

CONFIDENTIAL AND PROPRIETARY

This document contains information that is confidential and proprietary to Smith & Nephew PLC and Smith & Nephew, Inc. and is intended for use only by Smith & Nephew and its manufacturer. It shall not be reproduced or copied in whole or in part, nor shall the contents be disclosed by any means without prior written permission from Smith & Nephew, nor shall anyone make any use of it that is contrary to the expressed or implied wishes of Smith & Nephew.

Clinical Protocol	Study Number: OR3O.2019.10 (China)
Prospective, Multi-center, Randomized, Controlled Study to Evaluate the Safety and Efficacy of the OR3O™ Dual Mobility System versus conventional single bearing design Total Hip System in Primary Total Hip Arthroplasty (THA) Procedures	Version: 1.0, 18Aug2020
	Page: 53 of 90

- Full Analysis Set (FAS) Population: according to the basic principle of Intent-to-Treat (ITT) analysis, all randomly selected subjects with at least one validity evaluation will be included in FAS Population.
- Per-Protocol (PP) Population: The PP population is a subset of hips in the FAS population who do not have major protocol deviations and who satisfied all enrollment eligibility criteria. Criteria that can be regarded as major deviations will be formally classified on a case-by-case basis prior to the final study database lock.

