11. SAMPLE SIZE JUSTIFICATION

11.1 TOTAL SAMPLE SIZE

170 subjects who need unilateral hip joint replacement should be enrolled into the study - 85 subjects randomized per study arm.

The primary assumptions for sample size calculation are as below:

- Type I (α) error = 0.05
- Type II (β) error = 0.20 (Power = 80%)
- Margin of non-inferiority, $\Delta = -9.50\%$

Sample size calculation is based on the assumption that in order to be considered of comparable efficacy, study arm (dual mobility cohort) must obtain at least 90% of the efficacy in the controlled arm (conventional cohort). It is expected and further assumed that 95% of the Harris Hip Score at 12 months postoperative will have a rating of good or excellent (80-89, ≥ 90), then 76 evaluable subjects per group would be required to carry out the hypothesis testing at 12 months postoperatively. Assuming an attrition rate of 10% at 1 year, 85 subjects are needed per arm. It is

CONFIDENTIAL AND PROPRIETARY

This document contains information that is confidential and proprietary to Smith & Nephew PLC and Smith & Nephew, Inc. and is intended for use only by Smith & Nephew and its manufacturer. It shall not be reproduced or copied in whole or in part, nor shall the contents be disclosed by any means without prior written permission from Smith & Nephew, nor shall anyone make any use of it that is contrary to the expressed or implied wishes of Smith & Nephew.

Clinical Protocol	Study Number: OR30.2019.10 (China)
Prospective, Multi-center, Randomized, Controlled Study to Evaluate the Safety and Efficacy of the OR30™ Dual Mobility System versus conventional single bearing design Total Hip System in Primary Total Hip Arthroplasty (THA) Procedures	Version: 1.0, 18Aug2020
	Page: 59 of 90

planned to have 4 sites enrol on average, 43 subjects per investigational site and a min. of 20 subjects should be enrolled per site (overall subjects enrolled in the study of 170).

11.2 NUMBER OF SUBJECTS WITH EACH DISEASE IN CLINICAL STUDY AND REASON FOR DETERMINATION

In this clinical protocol, it is strictly required that patients should be enrolled in compliance with the inclusion/exclusion criteria. It can be considered that all the patients have the same type of disease, and are not further divided.

11.3 IN MULTI-CENTER CLINICAL STUDY, MINIMUM AND MAXIMUM NUMBER OF SUBJECTS IN EACH CLINICAL STUDY INSTITUTION AND JUSTIFICATION

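### The SAP reports the primary proportions only for implanted hips, although the protocol starts from randomised subjects; subjects randomised but given neither system drop out uncounted, and the SAP does not disclose the change

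*SAP*

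**What the plan says.** **Who is in the efficacy set.** Protocol 10.2 refers to intention to treat and states that "all randomly selected subjects with at least one validity evaluation will be included in FAS Population". It does not say whether a preoperative Harris Hip Score (HHS) is such an evaluation. SAP 7.2 cites the same principle, yet there "all implanted hips with at least one postoperative effectiveness, HRQoL or performance will be included in FAS Population".

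**Which set carries the primary endpoint.** Protocol 10.4.1 names the ITT population, which has no definition apart from the FAS. SAP section 7 names the FAS, with the per-protocol set in addition. SAP 7.10 names the SAF, which SAP 7.2 defines as implanted hips grouped by the device implanted.

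**When randomisation happens.** Protocol 8.5.2: "A randomization number is allocated only when subjects have signed the Informed Consent Form and satisfy all study eligibility criteria". Implantation is not a condition.

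**What may happen next.** Protocol 7.8.1: "Subjects may be withdrawn from having the study device implanted at a date close to surgery or during surgery". The reasons are at the investigator's discretion. Protocol 8.2.2 accepts that the surgeon cannot be blinded.

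**How such subjects are counted.** Protocol 7.8.1: "Subjects who provide informed consent but do not receive the study device for any reason will be considered a Screen Failure". Protocol 7.6 adds that "Screen Failures will not count into the total number of enrolled subjects" and that "Competitive enrollment continues until the completion of enrolled 170 subjects", where enrolled means implanted. Protocol 11.1 instead plans for "85 subjects randomized per study arm".

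**What the SAP declares.** SAP 7.15 lists only the loss of statistical testing after early termination.

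**The concern.** Randomisation protects the comparison only if subjects stay in the analysis in the arm to which they were assigned. Here a subject can leave both analysis sets between allocation and implantation. The decision may be taken by someone who knows the arm, certainly so during surgery. The subject is then classed as never enrolled and another is recruited in that place. If the reason is connected with the assigned device, one arm loses an unfavourable outcome and the other does not.

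The SAP already has a rule that would deal with this: SAP 7.3 scores a hip with no postoperative data as a failure. A subject who was never implanted does not reach that rule, because neither the FAS nor the SAF admits the subject. Nor does SAP 7.6 ask for randomised-but-not-implanted subjects to be tabulated by arm, so a reader of the report could not see an imbalance.

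A second route comes from SAP 7.10. Because the SAF groups by device received, a subject converted from one system to the other changes arm in the reported P1 and P0.

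**Working it through.** **1. The plan's own sample size.** Inputs from Protocol 11.1 and 11.4: success 95% in both arms, two-sided 5% (z = 1.960), power 80% (z = 0.842), and a requirement to keep 90% of control efficacy.

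- Ratio rule, testing p1 − 0.9·p0 > 0: n = 0.95 × 0.05 × (1 + 0.81) × (1.960 + 0.842)² / 0.095² = 75 per arm, against the stated 76.
- Fixed 9.5-point difference: n = 2 × 0.95 × 0.05 × (1.960 + 0.842)² / 0.095² = 83 per arm.
- Attrition: 76 / 0.90 = 84.4, so 85 per arm and 170 in total, as stated.

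The stated size is reproduced to within one subject on the ratio scale. The present point does not alter it.

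**2. Where a randomised subject ends up.**

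| Subject | Protocol FAS (10.2) | SAP FAS (7.2) | SAP SAF (7.2) | Counted in the 170 (Protocol 7.6) |
|---|---|---|---|---|
| Randomised, assigned system implanted, postoperative data | in | in | in | yes |
| Randomised, other system implanted | in, if evaluated | in, if postoperative data | in, by device received | yes |
| Randomised, neither system implanted | in only if a preoperative HHS counts | out | out | no, replaced |

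In the last row, if the preoperative HHS does count under the protocol, eligibility caps it at 79 (Protocol 7.2). Carrying it forward under Protocol 11.8 would give a failure. If it does not count, the subject is absent from the protocol FAS too.

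**3. Size.** The documents do not give the number k of test-arm subjects randomised but not implanted, so k is an assumption. Take n = 85 implanted per arm with 95% success in each, and score the k subjects as failures:

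- P1 = 0.95 × 85 / (85 + k)
- SE = √[P1(1 − P1)/(85 + k) + 0.95 × 0.05/85]
- Wald lower 95% limit = P1 − 0.95 − 1.96 × SE

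| k (test arm only) | P1 | Shift in P1 − P0 (points) | Lower limit (points) |
|---|---|---|---|
| 0 | 95.0% | 0.0 | −6.55 |
| 1 | 93.9% | −1.1 | −7.97 |
| 2 | 92.8% | −2.2 | −9.32 |
| 3 | 91.8% | −3.2 | −10.62 |
| 5 | 89.7% | −5.3 | −13.08 |

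The shift for one subject is 0.95/(n + 1): 0.95/86 = 1.1 points with 85 implanted. The trial stopped early and the number treated is not given. With an assumed 30 implanted per arm, 0.95/31 = 3.1 points, and P1 goes from 95.0% to 91.9%. Equal k in both arms lowers P1 and P0 alike and leaves their difference near zero.

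**The case against.** Several parts of the case on the other side stand.

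- **The protocol does not analyse everyone randomised.** A reader might infer that Protocol 10.2 keeps all randomised subjects and that the SAP removed them. The text does not support that: it requires at least one evaluation. If this means a postoperative one, non-implanted subjects are absent under both documents.
- **The exclusion does not originate in the SAP.** The screen-failure rule and continued enrolment come from Protocol 7.6 and 7.8.1. SAP 7.2 carries them into the FAS. The tension is already inside the protocol, between those sections and its own 10.2 and 11.1.
- **Conversion is not disappearance.** A reader might infer that a test device that cannot be fitted always leads to an excluded and replaced subject. Protocol 7.6 makes a subject a screen failure only if neither system is implanted. Someone converted to the other system stays in, although the study-device wording in 7.8.1 is less clear. The problem with conversions is grouping by device received.
- **No non-inferiority claim is at risk.** A reader might infer from the table that three exclusions overturn the trial's conclusion. SAP 7.10 says the test will not be performed. The crossing of −9.5 points at k = 3 belongs only to the test planned in Protocol 10.4.1 and 11.6, with every exclusion in one arm and every one a failure.
- **Scoring an unoperated subject as a failure is a choice.** It also penalises surgery cancelled for unrelated reasons.

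None of this removes the central facts. Both SAP sets start from implantation, one of them is described as intention to treat, P1 and P0 are still reported by arm, and the change from randomised to implanted is not recorded, although Protocol 11.9 asks that such changes be recorded with reasons.

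**Conclusion.** The point holds as a defect in the population on which the primary proportions are reported, and in its disclosure. Under either SAP section 7 or SAP 7.10, P1 and P0 describe implanted hips rather than the randomised arms. Under 7.10 they are also grouped by treatment received. The two SAP sections disagree on the set, and SAP 7.15 mentions neither this nor the departure from Protocol 10.2.

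The size is unknown. It is about 1.1 points of P1 for each excluded test-arm subject, assuming 85 implanted per arm, 95% success and failure scoring. It is larger with fewer treated subjects, and zero if nobody was randomised without being implanted. The documents do not show that any such withdrawal took place or that it favoured either arm; they show that the plan permits it and would not reveal it. The consequence under SAP v2.0 is possible bias in descriptive proportions. The correction is worth making because it is cheap and the two proportions are the trial's main efficacy output.

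**What to change.** 1. In SAP section 7, 7.2 and 7.10, state one primary population: all randomised subjects, in the arm to which they were randomised. Replace the sentence in 7.10 that assigns the primary endpoint to the SAF; changing 7.2 alone would leave the reported figures as they are.
2. Apply the existing SAP 7.3 rule, no postoperative data counted as failure, to randomised subjects who were not implanted. Show the implanted-only P1 and P0 beside the result as supportive.
3. In SAP 7.6, tabulate by arm and reason the subjects randomised but not implanted, and those who received the other system.
4. Record the population change and its reason in SAP 7.15.

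The cost is SAP wording, an addition to the disposition table and one further run of the primary summary. The randomisation system (Protocol 8.5.2) and the Screening and Enrollment Log (Protocol 7.4) should hold the needed data. The drawback is that P1 and P0 become slightly lower, because operations cancelled for unrelated reasons also count as failures; the supportive result shows by how much. With the trial already terminated early, amending the enrolment count in Protocol 7.6 is not needed.
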